- b. See Section 8.2.1.4 and the Site Imaging Manual for more information. CT chest, abdomen, and pelvis, or CT chest with MRI abdomen and pelvis. Neck CT and/or MRI for head and neck primaries. MRI brain: If no metastatic disease found, repeat only as clinically needed. If disease present, reimage Q12W with other staging scans. MRI spine as clinically needed. A CT scan of the extremity where the primary melanoma was diagnosed (or MRI if CT scan is contraindicated) should be performed at the investigator's discretion or when clinically indicated.
- c. EuroQoL 5 Dimension Questionnaire (EQ-5D-5L) should be completed during this phase at baseline (Cycle 1), during treatment at Cycles 9, 17 and 35, and at 24 and 48 weeks during first year off treatment. The EuroQoL EQ-5D-5L will be administered to all study participants, since it is considered acceptable to use for persons 12 years and older.

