### **Medical Conditions**

1. Has a known additional malignancy that is progressing or has required active antineoplastic therapy (including hormonal) within the past 5 years.

Note: Participants with basal cell carcinoma of the skin, squamous cell carcinoma of the skin, or carcinoma in situ (eg, breast carcinoma, cervical cancer in situ) that have undergone potentially curative therapy are not excluded.

Note: Participants with a history of nonulcerated cutaneous/acral primary melanoma <1 mm in depth with no nodal involvement are allowed in this study. Participants with any previous melanoma that was ulcerated,  $\geq 1$  mm in depth, with nodal involvement, metastasis, or was treated beyond surgical resection (for example, radiation therapy) are not eligible for this study. Participants with synchronous melanomas where lesions not under study are not ulcerated and <1 mm in depth are allowed on the study. Participants with a history of mucosal or uveal melanoma are excluded from this study even if diagnosis and treatment were completed >5 years ago.

2. Has a diagnosis of immunodeficiency or is receiving chronic systemic steroid therapy (in dosing exceeding 10 mg daily of prednisone equivalent) or any other form of immunosuppressive therapy within 7 days prior the first dose of study drug.

Note: The use of inhaled or topical steroids and systemic steroids at physiologic doses of corticosteroids (up to 5 mg/m^2/day prednisone equivalent with maximum dose of 10 mg daily) is allowed on study.

3. If participant received major surgery, they must have recovered adequately from the toxicity and/or complications from the intervention prior to starting study treatment.
4. A WOCBP who has a positive urine pregnancy test within 72 hours prior to randomization (see Appendix 5). If the urine test is positive or cannot be confirmed as negative, a serum pregnancy test will be required.

Note: In the event that 72 hours have elapsed between the screening pregnancy test and the first dose of study treatment, another pregnancy test (urine or serum) must be performed and must be negative in order for participant to start receiving study medication.

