**Diagnostic Assessments**

9. Has severe hypersensitivity ( $\geq$ Grade 3) to any pembrolizumab excipients.
10. Has an active autoimmune disease that has required systemic treatment in past 2 years (ie, with use of disease modifying agents, corticosteroids or immunosuppressive drugs). Replacement therapy (eg, thyroxine, insulin, or physiologic corticosteroid replacement therapy for adrenal or pituitary insufficiency) is not considered a form of systemic treatment and is allowed.
11. Has a history of (noninfectious) pneumonitis that required steroids or has current pneumonitis.
12. Has an active infection requiring systemic therapy.
13. Has a known history of human immunodeficiency virus (HIV) infection. No HIV testing is required unless mandated by local health authority.

PCI [REDACTED]

14. Has a known history of Hepatitis B (defined as Hepatitis B surface antigen reactive) or known active Hepatitis C virus (defined as Hepatitis C virus RNA [qualitative] is detected) infection. No testing for Hepatitis B and Hepatitis C is required unless mandated by local health authority.

PCI [REDACTED]

15. Has a history of active tuberculosis (*Bacillus tuberculosis*).

16. Has a history or current evidence of any condition, therapy, or laboratory abnormality that might confound the results of the study, interfere with the participant's participation for the full duration of the study, or is not in the best interest of the participant to participate, in the opinion of the treating investigator.
17. Has a known psychiatric or substance abuse disorder that would interfere with the participant's ability to cooperate with the requirements of the study.

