Participants assigned in the Part 1 initial treatment phase to the placebo arm who experience recurrence at any point during Part 1 therapy and follow-up and meet all crossover criteria will be offered crossover to pembrolizumab per dosing criteria in Section 4.3. Participants on the pembrolizumab arm during the initial phase of treatment who are greater than 6 months from last dose of pembrolizumab treatment and who experience a recurrence will be offered rechallenge with pembrolizumab per dosing criteria outlined in Section 4.3. Participants who have local recurrence, including local metastatic lymph nodes or distant metastases that are surgically resected may receive up to 17 cycles of therapy with pembrolizumab and participants with an unresectable local (regional metastatic lymph nodes, in-transit, satellite, and/or microsatellite metastases) or an unresectable distant recurrence may receive up to 35 cycles of therapy with pembrolizumab per Section 1.3.2.

All participants should have screening imaging within 28 days prior to C1D1 in Part 2 Crossover/Rechallenge phase. The Part 1 EOT scan can be used as baseline for Part 2 if done within 4 weeks of 1st dose in Part 2. Participants who have had surgical resection of lesion

captured on imaging must have a scan after surgery or radiation is complete to establish baseline imaging within 4 weeks prior to start of Part 2 therapy. Brain MRI must be obtained within 4 weeks prior to start of Part 2 treatment, unless contradicted; then CT may be acquired.

Disease recurrence/progression is confirmed by investigator (radiographically and/or by exam with subsequent biopsy) and RECIST 1.1/iRECIST will be used to identify disease progression in participants with metastatic/unresectable disease identified at the start of Part 2 therapy. Local recurrence should be documented with photo image.

Radiotherapy (palliative or adjuvant) is allowed prior to Part 2 (eg, post lymph node dissection radiotherapy when indicated). Radiotherapy has to be completed prior to first dose and complete wound healing is required prior to first dose. Radiotherapy is allowed during treatment in Part 2 as palliative therapy (treatment of pain, impending fracture, etc.) in participants with unresectable recurrence or metastatic disease. If surgery or radiotherapy other than described above is indicated while on Part 2 therapy Sponsor must be consulted.

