All eligibility criteria from Part 1 Sections 5.1 and 5.2 remain valid and must be reconfirmed prior to enrollment into Part 2 of the study with the EXCEPTION of:

- Inclusion Criteria 2, 3, 4 and 5
- Exclusion Criteria 5, 6 and 11

Participants must also meet the following requirements for entry into Part 2:

- Participant must have experienced an investigator determined/confirmed disease recurrence radiographically and/or by exam with subsequent biopsy. Local recurrence must be documented with photo image. Participants will only be eligible for Part 2 treatment after the first recurrence. If a participant experiences a second recurrence, they will not be eligible for Part 2. Participants who are less than 6 months from their last Part 1 pembrolizumab dose at the time of recurrence are not eligible for Part 2 treatment.

Note: Cutaneous lesions and other superficial lesions detectable only by physical exam must be categorized as nontarget lesions for Part 2 of the study.

- No new anticancer treatment was administered after the last dose of Part 1 study treatment.
- Participant is continuing from Part 1 and has completed 17 cycles of pembrolizumab or any number of cycles with placebo with no delays in treatment  $\geq 12$  weeks. If a  $\geq 12$ -week treatment delay has occurred, Sponsor approval must be obtained before moving into Part 2 of the study.

Note: For any participant who is not able to complete the required 17 cycles of pembrolizumab or have  $\geq 12$ -week treatment delay on placebo arm, a notification to the Sponsor is required to determine if it would impact their eligibility for entry into Part 2.

- Surgical resection or biopsy of unresectable or metastatic disease completed within 4 weeks of first dose.

- Full resection of lesions or biopsy of unresectable or metastatic disease confirmed by site pathologist to be melanoma.

Note: If biopsy is clinically contraindicated, investigators should seek Sponsor review and approval to start participant on Part 2 therapy.

If participant is identified to have a thoracic lesion or lymph node suspicious for a recurrence (especially if solitary lesion), it is encouraged that a biopsy be performed to confirm metastatic melanoma versus another lung primary malignancy versus a nonmalignant lung disease (eg, sarcoidosis).

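### Part 2 entry waives the current-pneumonitis exclusion, so no criterion expressly bars starting pembrolizumab with Grade 2 or higher disease that Table 4 would withhold or stop drug for

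*Protocol*

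**What the plan says.** Protocol Section 6.7 makes reconfirmation of the Section 5.1 and 5.2 criteria the default for Part 2, then lists exceptions by number. The exclusions lifted are "Exclusion Criteria 5, 6 and 11". Exclusion 11 reads "Has a history of (noninfectious) pneumonitis that required steroids or has current pneumonitis". No qualifier keeps either half of it in force.

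Section 6.7 adds its own entry requirements. The only toxicity they name is hypersensitivity of Grade 3 or higher. A closing paragraph bars participants who stopped Part 1 treatment for listed reasons, including unacceptable adverse events and intercurrent illness.

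Pneumonitis is treated explicitly elsewhere in the protocol. Table 4 in Section 6.6 withholds pembrolizumab at Grade 2 and discontinues it permanently at Grade 3 or 4 or on recurrent Grade 2. Section 7.1 lists recurrent Grade 2 pneumonitis as a reason to stop treatment. Section 6.5.2 ties the Table 4 guidance to events that the investigator judges related to pembrolizumab.

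**The concern.** Lifting exclusions 5 and 6 is unavoidable if participants already given anti-PD-1 therapy are to be rechallenged. Lifting the history limb of exclusion 11 has a similar logic, since it allows rechallenge after a resolved episode. Neither reason extends to the current-disease limb, and Section 6.7 offers no other.

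The list decides who starts open-label pembrolizumab, for up to 17 or 35 cycles, ordinarily within 4 weeks of recurrence. On its face it lets a participant begin drug with a condition for which the protocol would withhold or stop the same drug in someone already on it. What is at stake is the safety of a few participants, not inference.

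**Working it through.** There is no figure in the plan to reproduce. The check is a count followed by a comparison of texts.

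**1. Does any other criterion name pneumonitis?** Section 5.2 numbers its exclusions 1 to 19, and number 18 is marked as removed.

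- Active exclusions: 19 − 1 = 18.
- Lifted for Part 2 (5, 6, 11): 3.
- Retained: 18 − 3 = 15, of which 0 name pneumonitis.
- Requirements added in Section 6.7: 8 (first recurrence confirmed, no intervening anticancer treatment, Part 1 cycles completed, timing of resection or biopsy, pathology, brain metastases, performance status, hypersensitivity), of which 0 name pneumonitis.

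These counts establish that there is no express bar. They do not measure risk.

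**2. Entry rule against dosing rule.**

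| Current noninfectious pneumonitis | On treatment, drug-related (Table 4) | At Part 2 entry (Section 6.7) |
|---|---|---|
| Grade 1 | no action listed | no express bar |
| Grade 2 | withhold | no express bar |
| Recurrent Grade 2, or Grade 3 or 4 | permanently discontinue | no express bar |

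The two columns conflict only from Grade 2 upward.

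**3. What the remaining safeguards catch.**

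- *Exclusion 2* covers chronic steroids above 10 mg/day prednisone equivalent, or "any other form of immunosuppressive therapy within 7 days prior the first dose of study drug". Table 4 starts pneumonitis treatment at 1 to 2 mg/kg, which exceeds 10 mg/day for anyone heavier than 10 ÷ 1 = 10 kg, so for every participant here. Most steroid-treated cases are therefore caught, though whether a short course counts as chronic is arguable. Untreated disease is missed.
- *Exclusion 10*, "Has an active autoimmune disease that has required systemic treatment in past 2 years", may reach some immune-mediated cases, but only after systemic treatment.
- *Exclusion 12*, "Has an active infection requiring systemic therapy", does not reach noninfectious disease.
- *Exclusion 16* is wide enough to cover any condition where it "is not in the best interest of the participant to participate, in the opinion of the treating investigator". It depends on that opinion.
- *The Section 6.7 closing bar* covers participants whose Part 1 treatment was stopped for an unacceptable adverse event or intercurrent illness. It does not cover onset after Part 1 treatment ended, or a placebo participant who stopped because of recurrence.
- *Part 2 screening*: Section 6.7 says "All participants should have screening imaging within 28 days prior to C1D1 in Part 2 Crossover/Rechallenge phase", and footnote b of Section 1.3.2 specifies "CT chest, abdomen, and pelvis, or CT chest with MRI abdomen and pelvis". Adverse-event review, physical examination, vital signs and performance status are also scheduled. These can detect pneumonitis, but no entry rule is attached to the finding.
- *Sponsor review* is described unevenly. Footnote a of Section 1.3.2 requires approval, while Sections 6.7 and 8.1.11 also speak of notification. Under Section 8.4.1, nonserious events must be reported to 30 days after treatment and serious ones to at most 90, and pneumonitis is not a listed event of clinical interest in Section 8.4.7. A late nonserious case may therefore be missing from the reported data, although sites do review adverse events at follow-up visits.

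**4. Who is left.**

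- *Placebo crossovers with onset off treatment.* Table 4 does not apply, because the event cannot be related to pembrolizumab. The closing bar does not apply either. This is the main uncovered group.
- *Placebo participants with Part 1 pneumonitis judged unrelated and not severe enough to stop treatment.* Again neither rule applies.
- *Pembrolizumab completers with onset after cycle 17.* Table 4 and Section 7.1 already point against re-dosing for Grade 3 or 4 or recurrent Grade 2 events. The gap here is that those rules are not carried into the entry criteria.

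**The case against.** The strongest reply is that the gap is mostly one of wording. Exclusion 16 must be reconfirmed at entry and covers any condition that makes participation unwise. The grading scale in Appendix 4 treats Grade 2 as needing at least minimal intervention, so untreated Grade 2 disease at entry would already be a departure from normal management, and treated disease usually meets exclusion 2. Because causality is attributed before unblinding, on-treatment pneumonitis in a placebo participant could be judged drug-related and managed under Table 4. Section 6.7 also encourages biopsy of suspicious thoracic lesions to rule out nonmalignant lung disease. It states the aim of giving every participant access to pembrolizumab, which could justify leaving borderline cases to judgement.

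Much of this stands and limits the point. Two readings that a reader might infer are not supported:

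- *All current pneumonitis should be barred.* Table 4 lists no action at Grade 1, so barring new Grade 1 disease would deny drug to people whom the protocol would keep dosing.
- *The protocol freely permits re-dosing after severe pembrolizumab pneumonitis.* Section 6.7 bars those who stopped Part 1 for it, and Table 4 and Section 7.1 point against re-dosing later onsets.

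What the reply does not answer is why a general criterion is enough at Part 2 when it was not thought enough at Part 1, where exclusions 11 and 16 stood together. A site that sees number 11 lifted by name may reasonably take current pneumonitis to be acceptable, which weakens reliance on judgement.

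**Conclusion.** The point holds in limited form. Section 6.7 lifts the current-pneumonitis limb of exclusion 11, and no other Part 2 criterion expressly bars starting pembrolizumab with current noninfectious pneumonitis of Grade 2 or higher. Entry is thus looser than the protocol's own dosing rule for a drug-related event.

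The practical size is small. Indirect safeguards should catch most cases, and the uncovered group is mainly placebo crossovers with onset off treatment. The documents give neither a pneumonitis rate nor a count of Part 2 entrants, so no number is estimated.

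The documents give no reason for the waiver. That only its history limb was needed is an inference from the rechallenge design.

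It would be wrong to infer any threat to the trial's conclusions. RFS is settled at first recurrence, before Part 2 begins. SAP Section 3.6.1 follows DMFS and OS whether or not a participant enters Part 2. Alpha and sample size do not depend on this list. This is an inexpensive improvement to participant safety.

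**What to change.** Keep number 11 on the Section 6.7 exception list and add one sentence aligned with Table 4:

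> Exclusion 11 is waived except that participants with current pneumonitis of Grade 2 or higher, or pneumonitis still requiring more than 10 mg/day prednisone equivalent, or prior pembrolizumab-related pneumonitis meeting the Table 4 permanent-discontinuation criteria (Grade 3 or 4, or recurrent Grade 2), including onset after the last Part 1 dose, are not eligible for Part 2.

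This preserves rechallenge after a resolved single Grade 2 episode and does not exclude Grade 1 disease.

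The cost is one sentence in the next amendment, with the ethics review that Section 10.1.1 requires for significant changes, and a letter to sites. A very few participants may be delayed or denied Part 2 entry. The analysis plan needs no change.

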## **6.8 Treatment After the End of the Study**

The participant may be enrolled in an extension study upon completion of this study to continue protocol-defined assessments and treatment.

## **6.9 Clinical Supplies Disclosure**

The emergency unblinding call center will use the treatment/randomization schedule for the study to unblind participants and to unmask study treatment identity during Part 1 of this study. The emergency unblinding call center should only be used in cases of emergency (see Section 8.1.11). In the event that the emergency unblinding call center is not available for a given site in this study, the central electronic treatment allocation/randomization system (IRT) should be used in order to unblind participants and to unmask study treatment identity. The Sponsor will not provide random code/disclosure envelopes or lists with the clinical supplies.

Part 2 of the study is open-label; therefore, the participant, the study site personnel, the Sponsor and/or designee are not blinded. Study treatment (name, strength or potency) is included in the label text; random code/disclosure envelopes or lists are not provided.

See Section 8.1.11 for a description of the method of unblinding a participant during the study, should such action be warranted.

## **6.10 Standard Policies**

At the close of the study after unblinding, a letter is to be sent by the investigator to those participants who received placebos in the image of the competitor's product to provide the following advice:

“You have participated in a study conducted by the Sponsor. This is to advise you that you were among those who received a look-alike infusion provided locally by the clinical site to resemble the drug Keytruda (pembrolizumab) as much as possible. You did not receive the active drug Keytruda (pembrolizumab) as manufactured by Merck.”

## **7. Discontinuation of Study Treatment and Participant Withdrawal**

### **7.1 Discontinuation of Study Treatment**

Discontinuation of study treatment does not represent withdrawal from the study.

As certain data on clinical events beyond study treatment discontinuation may be important to the study, they must be collected through the participant's last scheduled follow-up, even if the participant has discontinued study treatment. Therefore, all participants who discontinue study treatment prior to completion of the protocol-specified treatment period will still continue to participate in the study as specified in Section 1.3 and Section 8.11.3.

Participants may discontinue study treatment at any time for any reason or be discontinued from the study treatment at the discretion of the investigator should any untoward effect occur. In addition, a participant may be discontinued from study treatment by the investigator or the Sponsor if study treatment is inappropriate, the study plan is violated, or for administrative and/or other safety reasons. Specific details regarding procedures to be performed at study treatment discontinuation are provided in Section 8.1.10.

A participant must be discontinued from study treatment but continue to be monitored in the study for any of the following reasons:

- The participant or participant's legally acceptable representative requests to discontinue study treatment.
- The participant's treatment assignment has been purposely unblinded by the investigator, MSD subsidiary or through the emergency unblinding call center during Part 1 prior to recurrence.
- Interruptions from the protocol-specified treatment plan for greater than or equal to 12 weeks between pembrolizumab doses for nondrug-related or administrative reasons require consultation between the investigator and the Sponsor and written documentation of the collaborative decision on participant management.

- A  $\geq$ 12-week break in pembrolizumab treatment due to a drug-related AE.
- The participant has a medical condition or personal circumstance which, in the opinion of the investigator and/or Sponsor, placed the participant at unnecessary risk from continued administration of study treatment.
- The participant has a confirmed positive serum pregnancy test.
- Participant with confirmed disease recurrence radiographically and/or by exam with subsequent biopsy while on Part 1 treatment with pembrolizumab or placebo must stop Part 1 study treatment. Participants on Part 1 treatment with placebo can be screened for Part 2 therapy with pembrolizumab.
- Confirmed disease recurrence identified by investigator (radiographically and/or by exam with subsequent biopsy) or confirmed progression per iRECIST if clinically stable during Part 2 treatment outlined in Section 8.11 (exception if the Sponsor approves treatment continuation).
- Any progression or recurrence of any malignancy, or any occurrence of another malignancy that requires active treatment (hormonal and/or antineoplastic therapy).
  - Exceptions to secondary malignancy include basal cell carcinoma of the skin, squamous cell carcinoma of the skin, new nonulcerated primary melanoma  $<$ 1mm in depth with no nodal involvement, or carcinoma in situ (eg, breast carcinoma, cervical cancer in situ) that have undergone potentially curative therapy. Exceptions should be discussed with the Sponsor prior to continuing therapy or remaining in follow-up.
  - Diagnosis of a new primary melanoma  $>$ 1mm or  $<$ 1mm with ulceration will result in discontinuation of therapy in Part 1 or Part 2 and make participant no longer eligible for Part 2 therapy.
  - Investigator may submit a Sponsor consultation form to request a participant be unblinded if the participant develops a second malignancy including a new primary melanoma  $>$ 1mm or  $<$ 1mm with ulceration.
- Noncompliance with study treatment or procedure requirements.
- Discontinuation of treatment may be considered for participants who have attained a confirmed CR and have been treated for at least 8 cycles (at least 24 weeks), receiving at least 2 doses of pembrolizumab beyond the date when the initial CR was declared.
- Recurrent Grade 2 pneumonitis.
- Completion of 17 cycles during Part 1 therapy.

Note: Participants who complete Part 1 therapy are still eligible for Part 2 therapy if they meet Part 2 eligibility guidelines. For any participant who is not able to complete the

required 17 cycles, a notification to the Sponsor is required to determine if it would impact eligibility for entry into Part 2.

- Completion of 17 cycles or 35 cycles with pembrolizumab as assigned in Part 2.

Note: The number of treatments is calculated starting with the first dose.

- Withdrawal of consent by participant to continue on study.

For participants who are discontinued from study treatment but continue to be monitored in the study, all visits and procedures, as outlined in the SoA, should be completed.

